3.3.2. EXCLUSION CRITERIA

Subjects will not be eligible for the study if any of the following criteria are present:

- 1. Will require revascularization in the target leg within 3 months of randomization;
- 2. In the investigator's assessment, will require an amputation in the target leg within 3 months of randomization:
- 3. Subjects with target foot ulcer with an etiology of vasculitis, pyoderma gangrenosum, necrobiosis lipoidica, hydrostatic pressure/venous insufficiency, any neoplasms (basalioma, Kaposi's sarcoma, squamous cell carcinoma, etc.), or due to a burn;
- 4. The study ulcer increased or decreased by 50% or more at baseline from screening (as assessed by comparison of post-debridement photos taken at screening and Day 0);
- 5. Evidence of active infection (e.g., cellulitis, osteomyelitis) or deep ulceration exposing bone or tendon in the foot planned for treatment;
- 6. Any gangrene;

- 7. Current fracture in the target foot;
- 8. Target ulcer located on an active (hot) Charcot foot;
- 9. Heart Failure with a NYHA classification of III or IV;
- 10. Body mass index (BMI) $> 45 \text{ kg/m}^2$ at Screening;
- 11. Stroke or myocardial infarction within last 3 months;
- 12. Unstable angina;
- 13. Uncontrolled hypertension defined as sustained systolic blood pressure (SBP) > 200 mmHg or diastolic BP (DBP) > 110 mmHg at baseline/screening evaluation;
- 14. Ophthalmologic conditions pertinent to proliferative retinopathy or conditions that preclude standard ophthalmologic examination;
- 15. Inflammatory disorder of the blood vessels (inflammatory angiopathy, such as Buerger's disease);
- 16. Subjects with advanced liver disease including decompensated cirrhosis, jaundice, ascites or bleeding varices;
- 17. Subjects currently receiving immunosuppressive medications chemotherapy, or radiation therapy;
- 18. Positive HIV or HTLV at Screening;
- 19. Active Hepatitis B or C infection as determined by Hepatitis B surface antibody (HBsAb), Hepatitis B core antibody (IgG and IgM; HBcAb), Hepatitis B surface antigen (HBsAg) and Hepatitis C antibodies (Anti-HCV), at Screening;
- 20. Clinically significant specific laboratory values at screening (e.g., Hemoglobin < 8.0 g/dL, WBC < 3,000 cells per microliter, platelet count < 75,000/mm³, AST and/or ALT > 3 times the upper limit of normal, or any other clinically significant lab abnormality which in the opinion of the investigator should be exclusionary);

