5.4. Derived Variables

Baseline Value

The last non-missing value prior to first dose of study drug. If a subject does not receive any study drug, baseline is the latest recorded measurement on or before the randomization date.

Change from Baseline Value

Change from baseline value is the arithmetic difference between a value of interest and a baseline value: Change from baseline value = (value of interest – baseline value).

Percent Change from Baseline Value

The ratio of the arithmetic difference between a value of interest and the baseline value to the baseline value multiplied by 100: (Change from Baseline / Baseline) \times 100.

Time to Complete Wound Closure

Time to complete wound closure is the time interval (in days) from Day 0 to the date of the first visit date within the allowed visit window where wound closure is so indicated by the investigator. If a subject has not experienced complete wound closure, the subject will be considered censored at the subject's end of study date.

Time to a major amputation in the target limb

Time to a major amputation in the target limb is the time interval (in days) from Day 0 to the earliest date of a reported AE of an amputation of the lower extremity above the ankle of the target limb.

Time to a minor amputation in the target limb

Time to a minor amputation in the target limb is the time interval (in days) from Day 0 to the earliest date of a reported AE of an amputation of a foot or any parts of a foot such as toes on the target limb.

Absolute Differentials

If not provided by the individual study center labs, values for the absolute differentials (i.e., neutrophils, lymphocytes, monocytes, eosinophils, and basophils) will be calculated by multiplying the WBC count by the corresponding percent differential in the total WBC count. Results should be rounded to the nearest hundred for units equivalent to $10^3/\mu L$.

Percent Differentials

If not provided by the individual study center labs, values for the percent differential (i.e., neutrophils, lymphocytes, monocytes, eosinophils, and basophils) will be calculated by dividing the corresponding absolute differential count by the total WBC count. Results should be rounded to the tenth of a percentage point.

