9.5.5. HbA1c, Serum Chemistry and Hematology

Shift tables (i.e., normal or abnormal at baseline versus normal or abnormal at follow-up in a 2-by-2 contingency table) based on the normal range will be provided to assess changes in laboratory values from baseline to follow-up results for each scheduled follow-up visit. Additionally, shift tables of severity (low, normal, high) at baseline vs low, normal and high at each scheduled follow-up visit will also be summarized for hematology and chemistry parameters. Low and high severities are with respect to the lower and upper limits of normal, respectively, while normal is within normal limits. The counts and percentage of subjects with each of the 4 possible "shift" outcomes will be calculated by treatment group.

Individual laboratory parameter values and changes from baseline will be summarized descriptively by treatment group at each scheduled follow-up visit.

Laboratory values and their center-specific normal ranges will be listed and summarized using SI units. For the WBC differentials, only the absolute values will be summarized; percent differentials, if provided by the study center, will be listed only.

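### SAP 5.4 rounds derived absolute WBC differentials to the nearest hundred in 10³/µL, which taken literally sets every plausible derived count to zero

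*SAP*

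**What the plan says.** SAP 5.4 (Derived Variables) applies to laboratories that report percentages without counts. The rule opens with its condition, "If not provided by the individual study center labs, values for the absolute differentials", and obtains each count by "multiplying the WBC count by the corresponding percent differential in the total WBC count". It then fixes the precision: "Results should be rounded to the nearest hundred for units equivalent to" 10³/µL. The next item in the same section gives the precision for derived percent differentials: "Results should be rounded to the tenth of a percentage point".

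SAP 9.5.5 says where the counts are used: "For the WBC differentials, only the absolute values will be summarized; percent differentials, if provided by the study center, will be listed only". It also says "Laboratory values and their center-specific normal ranges will be listed and summarized using SI units" and "Individual laboratory parameter values and changes from baseline will be summarized descriptively by treatment group at each scheduled follow-up visit". Normal/abnormal and low/normal/high shift tables against baseline are planned for hematology at each scheduled follow-up visit.

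Protocol 4.2.5 has hematology, including WBC with differential, done by a local laboratory at each site. Neither document restates or clarifies the rounding precision elsewhere.

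**The concern.** A differential count in 10³/µL (numerically the same as the SI unit 10⁹/L) is a small number, usually in single figures or a fraction. Rounding such a number to a multiple of one hundred removes all the information in it. The percent rule beside it has a workable precision, so this looks like a slip, but the text does not show which precision was intended. It could be hundredths, or 100 cells/µL expressed in the wrong unit. Two programmers could reasonably code different rules.

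What is at stake is the safety description of neutrophils, lymphocytes, monocytes, eosinophils and basophils. Percent differentials are listed but not summarised, so no second table would reveal or offset the loss. A real fall or rise in a subject whose counts are derived would disappear from the change-from-baseline summaries.

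**Working it through.** The plan gives no worked figure to reproduce, so the check applies its rule to numbers.

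**Inputs from the documents.** The rounding rule and the formula are in SAP 5.4. The only WBC level stated is the entry limit in Protocol 3.3.2, exclusion 20 ("WBC < 3,000 cells per microliter"), which is 3.0 in 10³/µL.

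**Assumed inputs.** WBC levels above 3.0, and differentials of 60% neutrophils, 30% lymphocytes, 6% monocytes, 3% eosinophils and 0.5% basophils. These are illustrative and do not come from the documents.

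**Formula.** Count = WBC × percent / 100. Rounding to a step s takes the multiple of s nearest to the count. With s = 100, a count goes to 0 whenever count / 100 < 0.5, that is, whenever the count is below 50.

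| WBC (10³/µL) | Cell type | Unrounded | Nearest 100 (literal) | Nearest 0.1 (100 cells/µL) | Nearest 0.01 |
|---|---|---|---|---|---|
| 3.0 | Neutrophils | 1.8 | 0 | 1.8 | 1.80 |
| 3.0 | Lymphocytes | 0.9 | 0 | 0.9 | 0.90 |
| 3.0 | Monocytes | 0.18 | 0 | 0.2 | 0.18 |
| 3.0 | Eosinophils | 0.09 | 0 | 0.1 | 0.09 |
| 3.0 | Basophils | 0.015 | 0 | 0.0 | 0.02 |
| 7.0 | Neutrophils | 4.2 | 0 | 4.2 | 4.20 |
| 7.0 | Lymphocytes | 2.1 | 0 | 2.1 | 2.10 |
| 7.0 | Monocytes | 0.42 | 0 | 0.4 | 0.42 |
| 7.0 | Eosinophils | 0.21 | 0 | 0.2 | 0.21 |
| 7.0 | Basophils | 0.035 | 0 | 0.0 | 0.04 |

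**Upper end.** At WBC 11, 20, 49.9 and 80 the literal rule still gives 0 for all five types. At 80, neutrophils are 80 × 0.60 = 48.0, still below 50.

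**Change between two derived visits.** Suppose WBC falls from 7.0 to 3.0 with neutrophils at 60%. The true change is 1.8 − 4.2 = −2.4. Under the literal rule it is 0 − 0 = 0.

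**Shift tables.** With both visits derived, neutrophils and lymphocytes are 0 at both. Wherever an absolute normal range is available they are classed low at baseline and low at follow-up, so a true move across a limit is not seen.

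**The 100 cells/µL reading.** With a step of 0.1 a count below 0.05 becomes 0.0. Basophils at 0.5% do so whenever WBC is below 0.05 / 0.005 = 10. At WBC 11 the basophil count is 0.055 and rounds to 0.1. The rounding error can reach 0.05 per value, more than the 0.035 basophil count at WBC 7.0.

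**The case against.** The strongest reply is that nobody would implement the literal rule. The neighbouring percent rule shows that sensible precision was intended, both alternative readings keep neutrophil and lymphocyte counts, and a table of zeros would be caught at the first program check. That is probably true, but it does not say which precision to use. Under SAP 1, a departure from the plan has to be documented in the study report.

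Two stronger readings are tempting and are not supported:

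- *That every differential count in the tables becomes zero.* The rule covers only values the laboratory did not provide. Supplied counts enter the same tables outside the rule. The documents do not say how many laboratories omit counts, so the affected share could be anything from 0% to 100%.
- *That derived counts shift to low.* A shift compares baseline with follow-up. A subject's samples would normally go to the same local laboratory, so both visits would be derived and both would be 0. That is low to low with no change. A false shift needs a supplied value at one visit and a derived value at another, and nothing in the documents suggests that this would happen. It is also not shown that a laboratory reporting only percentages would supply an absolute range.

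It is also fair that no document sets a required precision for basophils or eosinophils or names them as measures of interest, so the criticism of a 0.1 step carries less weight than the criticism of the literal rule.

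The impact is limited. SAP 9.5 plans no formal safety testing, and no efficacy endpoint uses differentials. SAP 1 counts 7 + 5 + 16 + 16 = 44 enrolled subjects. SAP 9.1 and 9.5.5 list the collected data, including percentages supplied by centres, so a derived count can be recovered from the listings. All of this bears on severity and leaves the text of the rule uncorrected.

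**Conclusion.** The rounding rule is wrong as written. Read literally, it sets every plausible derived absolute differential, and every change between two derived visits, to 0 in the only differential tables planned. The literal result rests on arithmetic alone and holds for any count below 50 × 10³/µL. Read as 100 cells/µL, it keeps the larger cell types and loses basophils at assumed WBC levels of 3.0 and 7.0; that part depends on the assumed 0.5% share.

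Severity is minor. The rule acts only on derived values, whose share is unknown, and only in descriptive safety summaries. Efficacy, eligibility and the analysis populations are untouched.

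**What to change.** In SAP 5.4, replace the nearest-hundred wording with an explicit number of decimals in 10⁹/L. Two decimals (0.01) would keep all five cell types usable. If the sponsor meant 100 cells/µL, the SAP should say one decimal and accept that basophils will often read 0.0.

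Add one sentence that changes from baseline and low/normal/high classes are computed from the unrounded derived value, with rounding for display only.

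The cost is one phrase, one sentence and about one line in the derivation program. No new data are needed.

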6. SAMPLE SIZE CALCULATION

Based on prior VM202 studies, the percentage of subjects achieving complete wound closure by the 4-month follow-up (i.e., 4-month responder rate) for VM202 (treatment arm) is assumed to range from 50% to 60%, and that for the placebo group is assumed to range from 20% to 30%. Table 4 below summarizes the statistical power for a sample size of 200 VM202 and 100 placebo subjects based on Fisher's exact test with a two-sided significance level of 0.05 for the statistical hypothesis specified in Section 4.1.

Table 4 Statistical power by estimated responder rates for Treatment (pt) and Control (pc) arms

Pt	рc	Statistical Power
0.50	0.20	>.999
0.50	0.25	0.985
0.50	0.30	0.898
0.55	0.20	>.999
0.55	0.25	0.999
0.55	0.30	0.982
0.60	0.20	>.999
0.60	0.25	>.999
0.60	0.30	0.998

Except for the assumption of $p_t = 0.50$ and $p_c = 0.30$, the statistical power for all assumptions of p_t and p_c is > 0.95. For the assumption of $p_t = 0.50$ and $p_c = 0.30$, the statistical power is about 90%.

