1. INTRODUCTION

This document outlines the statistical methods to be implemented during the analyses of data collected within the scope of Helixmith Co., Ltd. (formerly ViroMed Co., Ltd.) Protocol VMNHU-003/I [A Phase III, Double-Blind, Randomized, Placebo-Controlled, Multicenter Study to Assess the Safety and Efficacy of VM202 to Treat Chronic Nonhealing Foot Ulcers in Diabetic Patients with Concomitant Peripheral Arterial Disease (PAD)]. The purpose of this plan is to provide specific guidelines from which the analysis will proceed. Any deviations from these guidelines will be documented in the clinical study report.

Study enrollment commenced under Protocol VMNHU-003/C. There were 7 subjects enrolled under protocol version C, 5 enrolled under version E, 16 enrolled under version F, and 16 enrolled under version G; no subjects were enrolled under protocol version D, H or I.

Protocol VMNHU-003/E introduced the following changes to exclusion criteria in VMNHU-003/C:

- The study ulcer decreased by 50% or more at baseline from Screening (as assessed by comparison of post-debridement photos taken at Screening and Day 0); previously only ulcers that increased by 50% or more at baseline from Screening were excluded.
- Target ulcer located on an active (hot) Charcot foot; previously any Charcot foot was excluded.
- Body mass index (BMI) > 45 kg/m² at Screening; previously BMI > 35 kg/m² was excluded.
- All steroids except inhaled or ocular steroids; previously only high dose steroids were excluded.

Since these changes to the exclusion criteria were not expected to have a meaningful influence in favor of VM202 on the efficacy and safety parameters, no inferential analyses to account for the protocol version will be conducted. Descriptive summaries of the primary efficacy endpoint and overall adverse event rates will be produced for the subjects enrolled under different versions of the protocol.

Protocol VMNHU-003/F submitted with SAP revision C introduced the following changes to the inclusion criteria:

- the upper age limit for study participants will be raised to 80 years;
- addition of ABI > 1.4 (indicative of non-compressible vessels at the ankle) as a qualifying criterion for documented PAD;
- revision of 1 criterion for documented PAD to: history of lower extremity peripheral artery disease with previous related intervention in a leg.

Protocol VMNHU-003/G introduced the following changes to the exclusion criteria:

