- Removal of exclusion #2: unhealed prior amputation
- Removal of exclusion #5: more than one (1) ulcer on target foot
- Change to exclusion #22: removal of creatinine > 2.0 mg/dL as an exclusion
- Change to exclusion #23: glomerular filtration rate (GFR) \leq 30 mL/min/1.73 m² updated to \leq 30 mL/min/1.73 m²

Protocol VMNHU-003/H had no significant changes related to the SAP.

Protocol VMNHU-003/I being submitted with this SAP revision introduces the following changes:

- The definition of the intent-to-treat (ITT) population was broadened to all subjects who were randomized.
- The definition of the modified intent-to-treat (mITT) population was narrowed to include only those subjects who: 1) received any study drug injections, 2) had at least one post-baseline wound assessment, and 3) had no safety or efficacy parameter results before dosing that would have made the subject ineligible if the results had been known or disclosed at Screening
- Two per protocol (PP) populations have been defined. The former mITT population is now the first PP population (PP1), which includes all subjects in the revised mITT population who did not use the protocol-specified prohibited concomitant medications or treatments. The former PP population is now the second PP population (PP2), which includes all subjects in PP1 who:

 1) met the major protocol eligibility criteria, 2) received all injections based on the randomized treatment, 3) maintained standard of care for their wounds for the duration of the study, and 4) any other additional criteria established by the CDRC before unblinding.
- The primary endpoint has been modified to include all subjects with a target wound closure by the 4-month follow-up, and no longer requires that wound closure be confirmed at two consecutive study visits at least two weeks apart.

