3. STUDY DESIGN

This is a phase III, randomized, double-blind, placebo-controlled, multicenter, 7-month study designed to assess the safety and efficacy of intramuscular injections of VM202 in the calf of diabetic patients with chronic nonhealing foot ulcers and concomitant PAD. Subjects with confirmed PAD and diabetes aged \geq 18 years to \leq 80 years diagnosed with nonhealing foot ulcers will be screened for study eligibility after giving informed consent.

At Screening, standard of care will be initiated that will continue for the duration of the study, as follows:

- Surgical debridement of necrotic tissue or devitalized tissue
- Use of appropriate off-loading when ambulating
- Maintenance of moist wound environment

Three hundred patients (from up to 30 study centers) who meet the eligibility criteria will be randomized in a 2:1 ratio to one of two treatment groups: 200 patients with VM202 (16 mg) plus standard of care or 100 subjects with placebo plus standard of care, respectively. Safety will be monitored throughout the study by an independent Data Safety Monitoring Board (DSMB, Section 8.5).

Patients will receive intramuscular injections in the ipsilateral calf of the affected foot with the target ulcer of either VM202 or placebo on Day 0, Day 14, Day 28, and Day 42 as follows:

Treatment: Days 0, 14, 28, and 42

TREATMENT]	DOSE VM20	FINAL DOSE		
GROUP	DAY 0	DAY 14	DAY 28	DAY 42	VM202 (mg)
VM202	4	4	4	4	16
Placebo	0	0	0	0	0

0 indicates injections of Placebo

VM202 will be delivered in a solution of 0.5 mg VM202 / mL. All subjects will receive sixteen (16) 0.5-mL intramuscular injections of VM202 or placebo at each injection visit.

The schedule of study visits and the clinical parameters that will be measured at the visits are summarized in Table 1 to Table 3 below.

The subjects' target ulcer will be evaluated by photograph, surface area, depth, perimeter and volume measurements. Subjects must have a non-healing ulcer on Day 0 that meets study entry inclusion criterion # 5 and does not meet exclusion criterion #6 to be eligible for study participation. Subjects will continue to come to the clinic once a week for dressing changes and wound assessment until the ulcer has healed or study exit, whichever comes first. Measurement of the target ulcer will be performed at each follow-up visit until complete wound closure or study exit.

Further details on the study procedures and conduct are provided in the protocol.

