5.2. Study Points of Reference

Study Day 0

The date of the first study drug administration or the date of enrollment for subjects who were not administered any dose of study drug.

Study Day

For protocol defined assessments, the number of days from the day 0 visit to a date of interest, is calculated as:

Visit day = date of interest - date of study day 0.

Note that per CDISC dataset standards, the standard study day in the datasets will actually be calculated as:

If the date of interest is >= first dose date:

Study day= date of interest- date of first dose + 1 (there is no day 0)

If the date of interest is < first dose date:

Study day= date of interest- date of first dose + 1

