9.4.1.1. Primary Analysis of the Primary Efficacy Endpoint

The primary analysis for the responder rate will be based on the ITT population.

Fisher's exact test will be used to compare the responder rate between the treatment groups. The 95% confidence interval of the responder rate of each treatment group will be derived using the binomial distribution and the 95% confidence interval of the responder rate difference will be calculated.

Subjects whose status of wound closure cannot be assessed at 4 months (e.g., due to earlier discontinuation from the study), will be considered non-responders.

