10. INTERIM ANALYSIS

Due to the early stopping of the study, the protocol-specified interim analysis will not be conducted.

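### The SAP still states a 300-patient trial with about 90% power or more, although it also reports early stopping and enrolment counts that sum to 44; at that size power would be roughly 16% to 64%

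*SAP*

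**What the plan says.** SAP Section 3 describes the design in the future tense: "Three hundred patients (from up to 30 study centers) who meet the eligibility criteria will be randomized in a 2:1 ratio", with 200 on VM202 and 100 on placebo. SAP Section 6 adds that "Table 4 below summarizes the statistical power for a sample size of 200 VM202 and 100 placebo subjects", using Fisher's exact test at two-sided 0.05. Power there is 0.898 at responder rates of 0.50 v 0.30 and above 0.95 in the other eight scenarios.

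Two other places in the same SAP show that this size was not reached:

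- Section 1 reports "7 subjects enrolled under protocol version C, 5 enrolled under version E, 16 enrolled under version F, and 16 enrolled under version G", and adds that "no subjects were enrolled under protocol version D, H or I".
- Section 10 states: "Due to the early stopping of the study, the protocol-specified interim analysis will not be conducted".

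The Protocol keeps the 300-subject target in the Synopsis and in Sections 3.3 and 3.5.2, and the same power table in Section 6.1. It is version I, which accompanies this SAP: "Protocol VMNHU-003/I being submitted with this SAP revision introduces the following changes".

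The documents do not print 44 as a total, do not say that everyone enrolled was randomised, and give no arm sizes.

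**The concern.** The revision was updated for early stopping in one place and not in others. It cancels the interim analysis and gives enrolment by protocol version, while Sections 3 and 6 read as if recruitment to 300 were still ahead. Both sets of statements are current text, not a history of changes.

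What is at stake is how the primary result is read. The primary test remains a two-sided 0.05 Fisher test in all randomised subjects (SAP Sections 4.1, 7.1 and 9.4.1.1). A reader who takes Section 6 at face value would treat a non-significant result as coming from a trial with about 90% power or more, and so as fairly strong evidence against the assumed effect. At about 44 subjects that reading would be wrong.

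**Working it through.** **Inputs.** Two-sided alpha 0.05 (SAP Section 4.1). Fisher's exact test (Sections 6 and 9.4.1.1). VM202 rates 0.50, 0.55, 0.60 and placebo rates 0.20, 0.25, 0.30 (Section 6). Allocation 2:1 (Section 3). Enrolment 7 + 5 + 16 + 16 = 44 (Section 1).

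**Method.** For arm sizes n1 and n2, every 2×2 table (x, y) is enumerated, and

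power = Σ Bin(x; n1, p_t) × Bin(y; n2, p_c) × 1[Fisher p(x, y) ≤ 0.05].

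The two-sided p-value sums the probabilities of all tables no more likely than the observed one. The doubled one-sided p-value was run as a check.

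**Step 1: the plan's own figures, 200/100.** All nine cells of Table 4 reproduce within 0.02. The largest gap is at 0.50 v 0.30: 0.918 against 0.898 printed. The doubled p-value gives 0.897 there. Table 4 is right for the size it names.

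**Step 2: 44 subjects.** Two thirds of 44 is 29.3, so 29/15 is the closest split to 2:1. Assumption: all 44 were randomised.

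| VM202 rate | placebo 0.20 | placebo 0.25 | placebo 0.30 |
|---|---|---|---|
| 0.50 | 0.409 | 0.268 | 0.165 |
| 0.55 | 0.520 | 0.369 | 0.248 |
| 0.60 | 0.638 | 0.493 | 0.362 |

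Seven of the nine are below 0.5, one of them only just (0.493).

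**Step 3: sensitivity to the unknown split, total and Fisher convention.**

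| Arms | Power range | Below 0.5 | Range, doubled p | Below 0.5, doubled p |
|---|---|---|---|---|
| 29/15 | 0.165–0.638 | 7 | 0.147–0.618 | 8 |
| 30/14 | 0.175–0.646 | 6 | 0.153–0.624 | 8 |
| 28/16 | 0.194–0.693 | 6 | 0.184–0.687 | 6 |

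Over every split with a ratio from 1.6 to 2.4, power is 0.162–0.693 for totals of 40 to 44 and 0.137–0.696 for totals of 36 to 44. With doubled p-values the lowest values fall to 0.124 and 0.110. No scenario reaches 0.70. Power does not rise smoothly with the total, because the test is discrete.

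**Step 4: size needed.** At 2:1, the smallest total with at least 80% power is 54 for 0.60 v 0.20 (0.809), 102 for 0.55 v 0.25 (0.811) and 216 for 0.50 v 0.30 (0.801).

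**Step 5: precision.** The Wald half-width for the difference is 1.96 × √[p_t(1−p_t)/n1 + p_c(1−p_c)/n2]. At 0.50 v 0.30:

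- 29/15: 1.96 × √(0.25/29 + 0.21/15) = 0.295
- 200/100: 1.96 × √(0.25/200 + 0.21/100) = 0.113

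Over the nine scenarios, Wald gives 27 to 29.5 points at 29/15, and the expected Newcombe half-width is 25 to 27 points. Either method gives 10 to 11 points at 200/100.

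**Illustration.** A hypothetical 16/29 v 4/15 is a difference of 55.2% − 26.7% = 28.5 points, close to the middle scenario. Fisher p is 0.11, and an exact unconditional score-based 95% interval runs from about −4 to +55 points.

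**The case against.** A sample-size section records the basis of the design. Section 6 is worded conditionally on 200/100, is correct for that size, and claims nothing about the number achieved. The SAP does not hide the shortfall: enrolment and early stopping are both stated, Section 9.2 calls for disposition of all randomised subjects, and Section 9.4.1.1 says the "95% confidence interval of the responder rate difference will be calculated", which will show the imprecision. No decision in the SAP uses Table 4. The Protocol's target is prospective, and the text does not show whether version I was finalised before or after the decision to stop. Finally, 44 is a count of enrolled, not randomised, subjects.

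Much of this stands. Table 4 contains no error, no analysis is affected, and the Protocol needs no more than a note. The caution about 44 is also sound: Section 5.2 provides for "the date of enrollment for subjects who were not administered any dose of study drug", so enrolled and treated are not the same group, and the randomised count needs confirming.

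It does not remove the point. Facts given in Sections 1 and 10 do not correct an unmarked future-tense target in Section 3 or the only power figures in Section 6. The reader has to add the four counts and recompute the power to see that neither applies.

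**Conclusion.** The point holds, as a minor inconsistency. The size and power stated in SAP Sections 3 and 6 are not those of the trial that will be analysed, and the SAP does not say so. Under the SAP's own response rates, and assuming that all 44 were randomised at about 2:1, power is about 16% to 64% instead of about 90% or more. The conclusion survives other splits near 2:1, totals down to 36, and the other Fisher convention, which only lowers power. Dropout was not modelled because the documents give no rate; counting subjects with missing status as non-responders could reduce power further.

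Type I error, the endpoint, the populations, the test and the planned confidence intervals are unaffected.

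**What to change.** 1. In SAP Sections 3 and 6, mark the 300-subject target and Table 4 as the original plan, not reached because the study stopped early. One SAP sentence can cover the same figures in the Protocol Synopsis and Protocol Sections 3.3, 3.5.2 and 6.1.
2. Have the sponsor confirm the number randomised, then state it in the SAP. Do not print 44 as the ITT size before that.
3. At the confirmed number, and at the 2:1 ratio while the study is blinded, restate either power for the nine scenarios or the expected 95% half-width for the difference. Name the interval method, which Section 9.4.1.1 leaves open. This uses only the assumed rates and the allocation ratio, so it is not post-hoc power and reveals nothing about treatment. Actual arm sizes belong in the study report.
4. Optionally, add one sentence that a non-significant result is not evidence of no effect.

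The cost is a few sentences, one line or short table, and one confirmation from the sponsor. Data and analyses do not change; the stated power becomes less favourable.
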